2.3.3.2 Analysis using Worst Case of No Change or Observed Worsening

The negative binomial regression (NBR) primary analysis will be repeated penalizing patients in the 25 mg/kg/day or 50 mg/kg/day treatment arms who withdrew during the blinded phase treatment period. The following will be used as the analysis value for withdrawn patients in the active arms:

- Patients with a reduction (improvement) in percentage change from baseline during the blinded phase treatment period will be imputed by setting the treatment period denominator, used in the NBR offset, to 113 days and the seizure count set to a value giving the same daily average observed during the baseline period.
- Patients with an increase (worsening) in percentage change from baseline during the blinded phase treatment period will be imputed by setting the treatment period denominator, used in the NBR offset, to 113 days and the seizure count set to a value giving the same daily average observed during the treatment period.

The primary endpoint analysis will be repeated using the above imputation.

2.3.4 Onset of Efficacy

To estimate the time to onset of efficacy, the NBR primary analysis and the first key secondary endpoint of $\geq 50\%$ reduction in seizure frequency will be repeated by each cumulative day (e.g. Day 1, Day 1 and 2, Day 1, 2 and 3, etc.) of the blinded phase treatment period for TSC-associated seizures. In addition, the 25 mg/kg/day and 50 mg/kg/day treatment arms will be pooled and the above repeated for the first 10 days only.

2.4 Safety Evaluation

2.4.1 IMP Doses

For patients randomized to the 25 mg/kg/day or 50 mg/kg/day treatment arms, the following will be calculated for the blinded phase treatment period:

- Maximum dose achieved.
- Dose at the end of the period or time of withdrawal.
- Modal dose.

Unless missed doses or a dose reduction is recorded during the titration period, it will be assumed that patients were titrated according to the titration schedule stated in the protocol. The blinded phase treatment period will be defined as Day 1 to earliest of the day of last blinded phase dose or Day 113. The following will be summarized for patients randomized to the 25 mg/kg/day or 50 mg/kg/day treatment arms:

- Proportion of patients achieving the target maintenance dose.
- Proportion of patients at the target maintenance dose at the end of the blinded phase treatment period or time of withdrawal.
- Maximum dose achieved (mg/kg/day).
- Dose at the end of the blinded phase treatment period or time of withdrawal (mg/kg/day).
- Modal dose during the blinded phase treatment period (mg/kg/day).

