3. INVESTIGATIONAL PLAN

3.1 Trial Design

This multicenter trial consists of a randomized, placebo-controlled, double-blind phase followed by an open-label extension (OLE) phase.

Blinded Phase:

The blinded phase of the trial is a randomized, double-blind, parallel-group, 16-week comparison of two doses of GWP42003-P vs. placebo. Patients will complete a 1-week screening period and a 4-week baseline period before they are randomized to receive either 25 mg/kg/day GWP42003-P, 50 mg/kg/day GWP42003 P or placebo. Randomization will be stratified by age according to the following ranges: 1–6, 7–11, 12–17 years and 18–65 years. Patients will begin a 4-week dose escalation period, titrating up to their assigned dose, before continuing on a stable dose of blinded Investigational Medicinal Product (IMP) for 12 weeks.

Dose escalation for each patient is subject to the investigator's assessment of safety and tolerability. If a dose becomes poorly tolerated, the investigator may consider temporarily or permanently reducing the dose for the remainder of the trial.

Following completion of the blinded phase, patients will be invited to continue to receive GWP42003-P in an OLE.

Those patients opting not to enter the OLE will complete a 10-day taper period (down-titrating 10% per day for 10 days).

Open-label Extension Transition:

In order to maintain consistent exposure to IMP and maintain the integrity of the blind, patients will enter a 2-week blinded transition to the OLE. OLE IMP will be titrated up to 25 mg/kg/day whilst blinded IMP is simultaneously tapered down to zero. All patients will complete the transition and enter the OLE taking 25 mg/kg/day GWP42003-P:

- Patients from the placebo arm will titrate up to 25 mg/kg/day GWP42003-P.
- Patients from the 25 mg/kg/day GWP42003-P arm will continue to take 25 mg/kg/day GWP42003-P.
- Patients from the 50 mg/kg/day GWP42003-P arm will taper down (10% per day) to 25 mg/kg/day GWP42003-P.

Open-label Extension:

The OLE consists of a 3-week titration period followed by a maintenance period and a 10-day taper period. The initial OLE period will last for a maximum of 1 year.

Following titration according to the titration schedule, patients will continue with their optimal GWP42003-P dose. However, investigators may decrease the dose if a patient experiences intolerance, or increase the dose to a maximum of 50 mg/kg/day if required for better seizure control, until the optimal dose is found.

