5.6.2 Adverse Events

All reported AEs will be classified by system organ class (SOC), preferred term and lower level term using Version 19.1 of MedDRA.

Summaries will be presented by treatment arm as well as SOC and preferred term.

A blinded phase treatment emergent AE (TEAE) is defined as an AE with a start date on or after the first dose of IMP during the blinded phase up to and including the date of first dose of the OLE phase (OLE Day 1). An OLE phase TEAE is defined as an AE with a start date on or after the OLE Day 1. If an AE has a partial start date and it is unclear from the partial date (or the stop date) whether the AE started prior to or post first dose of IMP then the AE will be considered treatment emergent and if it is unclear which phase the event started, it will be assigned to both phases. If the start date of the AE is the same as the date of first dose of IMP from the blinded phase and the plausible relationship to IMP is marked on the CRF as "Prior to study medication" then the AE will not be considered treatment emergent.

An AE will be considered treatment-related if the plausibility relationship to trial medication is recorded on the CRF as 'yes'. If the data on plausibility relationship to trial medication is missing then the AE will be considered treatment-related.

An AE will be considered leading to permanent discontinuation of IMP if the action taken with IMP is recorded on the CRF as 'study medication stopped' or the outcome is recorded on the CRF as 'patient died'.

An AE will be considered leading to IMP dose reduction excluding permanent discontinuation if the action taken with IMP is recorded on the CRF as 'dose reduced', 'dose reduced temporarily' or 'study medication interrupted'.

An AE will be considered leading to temporary IMP dose reduction if the action taken with IMP is recorded on the CRF as 'dose reduced temporarily'.

An AE will be considered leading to permanent IMP dose reduction excluding permanent discontinuation if the action taken with IMP is recorded on the CRF as 'dose reduced'.

An AE will be considered fatal if the outcome is recorded on the CRF as 'patient died'.

The following summaries will be generated separately for the blinded and OLE phase (counts are by patient unless specified otherwise):

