5.7.5 Supplemental Drug Accountability Form

This form consists of 7 questions regarding various aspects of drug accountability and patient usage. It is completed as part of an interview with the patient/caregiver when a triggering drug accountability discrepancy is identified.

The triggering drug accountability discrepancies are as follows:

- Missing bottle(s).
- Compliance issues where one or more bottles are used compared to what was the expected use, according to the IVRS report and paper diary.
- Returned IMP supply with evidence of tampering.
- Greater than the target daily dose as recorded in the IVRS report and paper diary.

The number of patients with a completed form will be summarized separately for the blinded phase and OLE phase. The summary will be presented separately for all patients with a completed form and patients 12 years of age and older.

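### The addendum's default of scheduled titration would count a patient held below target as having reached it, if no missed dose or reduction is recorded

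*SAP*

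**What the plan says.** Addendum section 2.4.1 (IMP Doses) derives the maximum, end-of-period and modal dose for patients randomized to 25 or 50 mg/kg/day. The default is that "it will be assumed that patients were titrated according to the titration schedule stated in the protocol". Two exceptions lift it: missed doses, or a dose reduction, on record for the titration period. The section does not say how dose is derived once an exception applies.

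The same section then lists the summaries, among them "Proportion of patients achieving the target maintenance dose" and "Proportion of patients at the target maintenance dose at the end of the blinded phase treatment period or time of withdrawal". The addendum's Appendix 1 places them in Table A4, with the patient data in Listing A1.

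Main SAP section 3.1 describes the titration: "Patients will begin a 4-week dose escalation period, titrating up to their assigned dose". It adds a condition: "Dose escalation for each patient is subject to the investigator's assessment of safety and tolerability".

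**The concern.** Section 3.1 foresees that a patient may not be moved up a step. The addendum's rule has no place for that patient. Someone kept at a lower step who takes every dose as instructed has missed nothing. On the plain meaning of the words the dose was also not reduced; it was not raised. The default then assigns the scheduled doses up to the randomized target.

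The proportion reaching target is meant to show whether titration succeeded, and here success is what is assumed when nothing is recorded. The addendum supports a summary of clinical efficacy, and its section 2.3.3 reports more withdrawals in each active arm than on placebo. A reader of that summary will therefore want to know what dose patients reached. Table A4 is the only planned blinded-phase table that would say so in mg/kg/day.

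**Working it through.** The SAP gives no figure to reproduce. The check sets the sections side by side and then shows a range under stated assumptions.

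**1. Which patients does the rule misclassify?**

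| Patient | Under addendum 2.4.1 | Correct? |
|---|---|---|
| Missed doses or reduction recorded in titration | Taken off the assumed schedule | Intended, though the derivation is not given |
| Stops IMP before titration ends | Dose window closes at the last blinded dose, so not counted at target | Yes |
| Held for a time, later reaches target and stays there | Counted as achieving target | Yes; only the timing, and rarely the modal dose, is wrong |
| Held below target throughout, hold recorded as a reduction | Taken off the assumed schedule | Intended |
| Held below target throughout, no missed dose or reduction recorded | Counted as achieving and remaining at target | No |

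Only the last row puts the proportions at target wrong.

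**2. Modal dose after a temporary hold.** The treatment period is Day 1 to Day 113 (main SAP 5.1.3.4). Take a patient who completes it, reaches target on day T and stays there. Days at target are 113 − T + 1 = 114 − T. Days at any one lower step are at most T − 1. Target is certainly the modal dose if 114 − T > T − 1, that is if T < 57.5. A patient at target by Day 57 has 57 days there against at most 56 at any lower step. The scheduled end of titration is Day 28 (5.1.3.5), so a hold would have to last about four weeks beyond that before the mode could be wrong.

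**3. Does another blinded-phase table show the dose reached?**
- Table 10.2 gives expected volume from Day 1 weight and the randomized dose level (5.6.1).
- Table 10.1 and the compliance formula count dosing days, not dose level (5.6.1).
- Tables 12.5 to 12.10 count adverse events by the action taken, such as those "recorded on the CRF as 'dose reduced', 'dose reduced temporarily' or 'study medication interrupted" (5.6.2). A hold not coded that way does not appear.

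None of these supplies the dose reached.

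**4. Illustrative size.** Let h be the number in an arm who fall in the last row of the table. With 70 planned per arm (main SAP 3.2), the overstatement of the proportion at target is 100 × h / 70 percentage points.

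| h (assumed) | 1 | 3 | 5 | 7 | 10 | 14 |
|---|---|---|---|---|---|---|
| Overstatement, points | 1.4 | 4.3 | 7.1 | 10.0 | 14.3 | 20.0 |

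This converts an assumed count into a percentage; it is not evidence of how often holds occurred. For each such patient the maximum, end and modal doses are too high by the gap between the dose held and the target.

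**The case against.** The strongest reply is that the key premise lies outside the document. The response to poor tolerability that section 3.1 names is a temporary or permanent dose reduction. Sites may have recorded a held step as a reduction, and the exception would then catch it. The CRF and its instructions are not shown. The action categories in section 5.6.2 define adverse event tables and do not claim to list every CRF option, so the absence of a held escalation there proves little. This stands as a limit on how many patients are affected. It does not close the gap, because the addendum does not say that a reduction includes a step not taken.

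Three stronger readings are tempting, and the SAP does not support them.

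- *The rule can only err upward.* That is true for a held escalation but not in general. Section 5.7.5 foresees intake described as "Greater than the target daily dose as recorded in the IVRS report and paper diary"; for such a patient the assumed schedule would understate the maximum dose.
- *The trial holds daily dose data and sets them aside.* Section 5.7.5 mentions an IVRS report and paper diary, and Listing 10.2 is titled Exposure by Time. These suggest a dose record but do not establish an analysable daily dose in mg/kg. Section 5.6.1 builds exposure from the last-dose date, the missed-doses log and an expected volume, with no daily dose variable.
- *Efficacy would be credited to a dose some patients never took.* Efficacy is analyzed by randomized arm in the ITT set (main SAP 5.2.2, addendum 2.2), and no efficacy analysis uses Table A4.

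It is also fair that the assumption is stated openly, that it concerns titration, and that nothing says later recorded dose changes are ignored. Tables on discontinuation and dose reduction describe tolerability without relying on this rule.

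**Conclusion.** The concern holds in a limited form. As written, a patient held below target through the blinded period, with neither a missed dose nor a reduction recorded, is reported in Table A4 as achieving and remaining at target, with the maximum, end and modal doses too high. Temporary holds and stops during titration are largely handled correctly.

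The size is unknown. It depends on how many holds lasted throughout and on whether sites recorded them as reductions, and the SAP shows neither. A larger effect in the 50 mg/kg/day arm is plausible but not documented. The effect is confined to post-hoc descriptive dose summaries (Table A4, Listing A1); the primary and key secondary tests are untouched. The change is still worth making, because no other planned table would reveal the error and the repair is small.

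**What to change.** Amend addendum section 2.4.1 as follows:

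- Treat a recorded held or delayed escalation as an exception alongside missed doses and reductions, and say how dose is derived when any exception applies.
- Derive dose from recorded data: dose-change records, and the diary, IVRS or exposure data where these hold the dose level.
- Assume the schedule only where no dose record exists.
- Report in Table A4, by arm, how many patients' doses rest on the assumption.

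If no usable dose-level record exists, the definition of the exceptions and the count of assumed patients can still be given. This changes a derivation only and touches no dosing or titration rule. The cost is addendum wording and minor programming, and possibly a slightly lower reported proportion at target.

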3. AMENDMENTS

Notable changes to the SAP addendum between approved versions are given below. Minor changes, clarifications and corrections are not listed.

Date	Section	Description of Change
------	---------	-----------------------

None

4. ATTACHMENTS AND APPENDICES

Appendix 1 List of Tables and Figures

Lists of the tables, figures and listings to be provided are given below in Table 1 Table 2 and Table 3, respectively.

Table 1 List of Tables

Table Number	Title	Analysis Set
Table A1.1	Analysis of Time to TSC-associated Seizures from the Start of the Treatment Period	ITT Analysis Set
Table A1.2	Analysis of Time to Total Seizures from the Start of the Treatment Period	ITT Analysis Set
Table A2	Negative Binomial Regression Analysis of TSC-associated Seizure Count During Baseline and Treatment Periods Using Worst Case of No Change or Observed Worsening for 25 mg/kg/day or 50 mg/kg/day Patients who Withdrew During the Treatment Period	ITT Analysis Set
Table A3.1.1	Negative Binomial Regression Analysis of TSC-associated Seizure Count During Baseline and by Cumulative Day in the Treatment Period	ITT Analysis Set
Table A3.1.2	Analysis of TSC-associated Seizure Treatment Responders During the Treatment Period by Cumulative Day	ITT Analysis Set
Table A3.2.1	Negative Binomial Regression Analysis of Convulsive Seizure Count During Baseline and by Cumulative Day in the Treatment Period - 25 mg/kg/day and 50 mg/kg/day Pooled	ITT Analysis Set
Table A3.2.2	Analysis of TSC-associated Seizure Treatment Responders During the Treatment Period by Cumulative Day - 25 mg/kg/day and 50 mg/kg/day Pooled	ITT Analysis Set
Table A4	Summary of Dose During the Blinded Treatment Phase	Safety Analysis Set

Table 2 List of Figures

Figure Number	Title	Analysis Set
Figure A1.1	Cumulative Distribution Function for TSC-associated Seizures During the Treatment Period - Patients Taking Clobazam	ITT Analysis Set
Figure A1.2	Cumulative Distribution Function for TSC-associated Seizures During the Treatment Period - Patients Not Taking Clobazam	ITT Analysis Set
Figure A2.1.1	Kaplan-Meier Plot of Time to 10th TSC-associated Seizure from the Start of the Treatment Period (Day 1)	ITT Analysis Set
Figure A2.1.2	Kaplan-Meier Plot of Time to 20th TSC-associated Seizure from the Start of the Treatment Period (Day 1)	ITT Analysis Set
Figure A2.2.1	Kaplan-Meier Plot of Time to 10th Total Seizure from the Start of the Treatment Period (Day 1)	ITT Analysis Set
Figure A2.2.2	Kaplan-Meier Plot of Time to 20th Total Seizure from the Start of the Treatment Period (Day 1)	ITT Analysis Set

Table 3 List of Listings

Figure Number	Title	Analysis Set
Listing A1	Dose During the Blinded Treatment Phase	Safety Analysis Set
